Utilizing All Health System Contacts to Offer Postpartum Family Planning (PPFP) to Pregnant Women and Women within Twelve Months Postpartum in Ethiopia

Study Protocol

Jhpiego

Unique Protocol ID: IRB00007143

February 2, 2018

JHSPH IRB Research Plan for New Data Collection

PI Name: [name]
Study Title: Utilizing All Health System Contacts to Offer Postpartum Family Planning (PPFP) to Pregnant Women and Women within Twelve Months Postpartum in Ethiopia
IRB No: IRB00007143
PI Version No./Date: V3_February 2, 2018

I. Aims of the Study: Describe the aims/objectives of the research and/or the project's research questions or hypotheses.

The objectives and sub-objectives of this study are to:

- 1) Assess the effect of contacts that women/couples have with the health system (from the *kebele* [sub-district] level to the health facility level and back), into which postpartum family planning (PPFP) messages are systematically integrated, on uptake of PPFP through 12 months postpartum in Ethiopia. These health contacts span several levels: at health facilities from trained health professionals, and at community settings from Health Extension Workers (HEWs) and Health Development Army (HDA), a cadre of community volunteers.
 - a. Assess the extent and type of existing contacts that women/couples have with the health system during pregnancy, birth, and in the postpartum period and the degree to which they receive PPFP messages during these health contacts.
 - b. Assess the relationship between frequency and type of contact to uptake of PPFP and recommended child feeding and immunization practices (estimate the dose-response effect of each additional health contact).
- 2) Estimate the added effect of a community-based intervention (i.e. beyond the health center) to promote PPFP messaging at antenatal and postpartum contact points by community health workers (HEWs, HDA) on uptake of postpartum family planning through twelve months postpartum in two clusters of health center and health posts, as compared to health center-only PPFP counseling and services in two comparison clusters.
 - a. Measure "baseline" PPFP uptake through recall of women with prior birth history and their PPFP use after those recall births (sub-sample of women with prior birth history)
 - b. Prospectively assess uptake of PPFP among postpartum women by type of health contact, timing postpartum, and contraceptive method

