- 3) Explore acceptability and feasibility among HC providers and health extension workers of using record keeping and review processes to track women's decision-making and contraceptive use from pregnancy through to 12 months postpartum,
 - a. Test provider/health extension worker (HEW)/health development army (HDA) use of health record keeping systems as a tool for identifying women who need additional PPFP counseling (prenatal).
 - b. Test use of a monthly data review process to combine HEW and HDA health records of pregnant and recently delivered women and their babies to ensure maximum coverage of critical health practices including antenatal care (ANC), postnatal care (PNC) home visits, PPFP uptake, immunization, infant feeding, etc.
- 4) Explore factors influencing women's/couples' adoption of PPFP during the first twelve months postpartum.

In both intervention and comparison sites, the study will implement the current Government of Ethiopia policy and standard of care concerning systematic integration of PPFP messages and services within antenatal care, labor and

delivery, postnatal care as well as a new proposed targeting of women bringing infants for immunization services with PFP messages and referrals.

II. Background and Rationale: Explain why this study is being done. Summarize briefly what is already known about the issue and reference previously published research, if relevant.

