The Ethiopian health system envisages that a number of health contacts should occur for women and babies from pregnancy through to the extended postpartum. Figure 1 below illustrates these contacts.

Figure 1: Possible Contacts with the Health System for Pregnant Women in Ethiopia

Month	4	5	6	7	8	9		1	2	3	4	5	6
Client	Pregnancy						Birth	Postpartum Period					
HDA	x	x	x	x	x	X	Home	X	x	x	x	x	x
HEW	Quarterly visits: 2-3 times during last two trimesters of pregnancy							Quarterly visits: 2-3 times during first 12 months postpartum					
HC	ANC1 Before end of 4 th month		ANC2 24-28 weeks	ANC3 32 weeks	ANC4 36 weeks	Facility		PNC w/in 48 hours; w/in 6 weeks					
								DPT1 6 weeks		DPT2 10-14 weeks		DPT3 14-22 weeks	

About 84% infants receive at least one dose and more than 60% receive two doses of basic vaccines. A substantial number of mothers also seek care for their child's fever, diarrhea and other illness from health providers. This study will take these contact occasions as opportunities for promoting PFP, but also to reinforce the need to fully vaccinate children.

III. Study Design

- A. Provide an overview of your study design and methods. The study design must relate to your stated aims/objectives. Details will be requested later. If your study also involves analysis of existing data, please complete Section XI, "Secondary Data Analysis of Existing Data" in the last part of this research plan. If your study ONLY involves analysis of existing data, please use the research plan template for secondary data analysis (JHSPH IRB Research Plan for Secondary Data Analysis of Existing Data/Specimens).

This implementation research will use a quasi-experimental mixed method design with two arms. The intervention arm will have integrated PFP messages at each level of health system contacts. The control arm will continue to deliver the existing FP services at primary health care centers only.

The primary study population is a cohort of pregnant women, enrolled between the 2nd and 3rd trimester of pregnancy in both arms, who will be followed to twelve months post-partum. We will interview the women at study enrollment and at the end of the study. We will track women's contacts with the health system, particularly regarding PFP counseling, decision making and contraceptive adoption, through chart reviews of routinely collected facility and community based health records and registers (e.g. family folders that may be modified for study).

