Appendix 1. FP [and MNCH] Tasks by type of facility and cadre

Level of facility	Type of health personnel available	FP Services*	MNCH Services
Health Post	Health Extension Workers	
 • Counsel on FP and other RH issues • Counsel on natural FP methods • Provide injectables • Insert Implanon • Refer to health center for other long-acting and permanent methods • Do planning based on local data 	
 • Limited ANC + Referral to Health Center • PNC • Immunization
Health Center	Health Officers (HOs), Midwives, Clinical Nurses, Public Health Nurses, Laboratory Technicians	
The above activities, plus:
 
 • Conduct general physical and pelvic examinations, including VIA/VILI • Insert and remove implants • Insert and remove IUCD • (Where a trained GMP/HO is available), provide tubal ligation and vasectomy • Manage complications and side effects • Provide syndromic management of STIs • Provide HCT, including care • Train community-level workers and junior health professionals in FP • Conduct monitoring and facilitative supervision 	
The above activities, plus
 
 • Labor and delivery (BeMONC)
Primary Hospital	Non physician clinicians, GMPs, HOs, Midwives, Clinical Nurses, Public Health Nurses, Laboratory Technicians	
The above activities, plus:
 
 • Provide permanent methods of contraception • Receive referrals • Manage complications and side effects • Do work-ups for infertility 	
The above activities, plus:
 
 • Caesarean section • Blood transfusion • Receive Referrals • Manage Complications • KMC
General and Referral Hospitals	Obstetrician-Gynecologists, GMPs, HOs, Midwives, Clinical Nurses, Public Health Nurses, Laboratory Technicians	
The above activities, plus:
 
 • Manage infertility • Manage complicated STIs • Manage complications and side effects of contraceptive methods • Manage ROCs Perform research 	
The above activities, plus:
 
 • Emergency obstetric and newborn referral service

*Content on FP services taken verbatim from “National Guidelines for Family Planning Services in Ethiopia”, Federal Ministry of Health, 2011.

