## Analysis Plan

### Utilizing All Health System Contacts to Offer Postpartum Family Planning (PPFP) to Pregnant Women and Women within Twelve Months Postpartum in Ethiopia

This plan describes how data collected through different methods will be analyzed after cleaning in order to meet these research objectives:

1. Estimate the added effect of the community-based intervention by comparing uptake of PPFP through 12 months postpartum in intervention and comparison sites (“intent to treat” analysis)
2. Assess the effect of systematically integrating PPFP messages into contacts with the health system on uptake of PPFP through 12 months postpartum using a dose-response analysis based on the number of contacts (“per protocol” analysis)
3. Explore the feasibility of tracking PPFP and reviewing data at health centers and HEWs and volunteers using record keeping and review processes to track women's decision-making and contraceptive use from pregnancy through 12 months postpartum
4. Explore factors influencing women's/couples' adoption of PPFP during the first 12 months postpartum

Quantitative and qualitative data analysis will be triangulated to help interpret results and provide deeper insights on study objectives.

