#### A. Quantitative interviews with Women:

After data have been thoroughly examined for quality, the study team will perform exploratory data analysis of key variables such as checking frequency distributions, measures of variability, central tendency, and data outliers. We will also check for incomplete data and consider strategies to handle missing values such as undertaking an imputation strategy and weighting adjustments for non-responses.

We will compare differences by study arm for key variables. Analysis will account for clustering of variables at kebele (village) level using the Taylor linearization method. Differences between the arms for categorical variables will be assessed using the Pearson chi-squared test with the Rao-Scott correction. Differences in continuous variables will be assessed using an adjusted t-test. In case of substantial differences between the study arms, we will perform propensity score matching and perform the analysis with inverse probability weights.

Key descriptive variables:

- Sociodemographic data such as age, marital status, education, and socioeconomic status (nationally representative SES will be determined using the EquityTool described here: <http://www.equitytool.org/>)
- (Baseline only) Proportion of pregnant women with non-first pregnancies (non-primiparous) who previously used family planning
- Number of health system contacts where FP was discussed or provided, by type of contact (ANC, PNC, immunization, etc) and provider (facility provider, HEW, volunteer)
- Proportion of postpartum women who chose a method prior to delivery, by method, and received chosen method
- Proportion of postpartum women who used FP during the first 12 months after giving birth, by method
- Reasons for starting and stopping contraceptive methods and duration of use

- Initiation and duration of exclusive breastfeeding and lactational amenorrhea (LAM); average/median duration of postpartum amenorrhea, PP sexual initiation/PP abstinence
- Partner communication about family planning

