We will fit multivariable logistic regression models for the primary and secondary binary outcomes (see below) to examine differences between the study arms, adjusted for confounding covariates and clustering at kebele level. We will also conduct a “per-protocol analysis” by examining the “dose-effect” of health system contacts on the primary and secondary outcomes, regardless of study arm. We will run two dose-effect models, looking at the association between the outcomes and 1) the total number of contacts and 2) the number of contacts during which FP was discussed as reported by the woman. For the secondary outcome, we will only include contacts during pregnancy since contacts after the birth would not have a temporal effect on whether the woman chose a method prior to delivery.

- Primary outcome:
  - Proportion of interviewed postpartum women who used a modern family planning method within 12 months after giving birth
- Secondary outcome:
  - Proportion of interviewed postpartum women who chose a method prior to delivery

We will also conduct time-to-event analyses using life-table method and use a log-rank test to test for differences in survival distributions between the study arms in terms of the timing of FP uptake after birth. We will perform multivariable hazards model (Cox’s proportional model or parametric model with Weibull distribution in case of non-normality in hazards function) for adjusting confounding covariates and clustering effects.

Additionally, we will run hazards regression models for women who initiated exclusive breastfeeding/LAM after birth to test for differences between arms in the duration of exclusive breastfeeding/LAM use.

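### The primary-outcome dose-effect models set no time window on contacts, so contacts made after method uptake count towards the dose

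*SAP*

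**What the plan says.** SAP section A (Quantitative interviews with Women) describes a per-protocol analysis, pooled over arms, that relates the primary and secondary outcomes to "the total number of contacts and 2) the number of contacts during which FP was discussed as reported by the woman". The next sentence adds a timing rule for one outcome: "For the secondary outcome, we will only include contacts during pregnancy since contacts after the birth would not have a temporal effect". The primary outcome is use of a modern method at any time in the 12 months after birth, and no equivalent rule follows for it.

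The aim is worded as an effect. SAP objective 2 is to assess the effect of integrating messages into contacts "on uptake of PPFP through 12 months postpartum using a dose-response analysis based on the number of contacts". Protocol section I, objective 1b, is to "estimate the dose-response effect of each additional health contact".

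No other place supplies a window. The protocol's data analysis plan (section V.C, item 4) mentions only a dose-effect of contacts. The SAP's descriptive variable, "Number of health system contacts where FP was discussed or provided, by type of contact", is not limited in time. SAP section C adds stock-outs and counselling quality to the per-protocol analyses but says nothing on timing. The planned hazards models compare arms and do not name contacts as an exposure.

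**The concern.** The SAP's reason for restricting the secondary outcome applies equally to the primary one: a contact that follows the event cannot have produced it. A woman may start a method at delivery, at postnatal care or at an immunization visit (protocol section V.C, item 4). She can go on having contacts for the rest of the year; protocol Figure 1 shows, for health extension workers, "Quarterly visits: 2-3 times during first 12 months postpartum". All of these enter her dose, as do visits made only to collect a method already chosen.

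At stake is the reading of SAP objective 2 and protocol objective 1b. If adopters have more contacts because they adopted, the slope suggests that contacts work when they may not. If non-adopters are followed up more, it can hide or reverse a real benefit.

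**Working it through.** **1. The text, side by side.**

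| Outcome | When the event can occur | Contacts counted |
|---|---|---|
| Secondary: method chosen before delivery | Pregnancy | Pregnancy only, temporal reason given |
| Primary: modern method within 12 months | Birth to month 12 | No limit stated |

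**2. Inputs for an illustration.** The documents give no figure for the dose models, so only the sample size and uptake come from them. Protocol section III.B uses 20% and 10% uptake, two-sided alpha 0.05, power 80% and a design effect of 1.5. The plan's figure reproduces:

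n = [1.96 × √(2 × 0.15 × 0.85) + 0.8416 × √(0.16 + 0.09)]² / 0.10² = 199 per arm; 198.96 × 1.5 = 298.4, so 299; 299 / 0.8 = 374, against 375 stated.

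Hence 2 × 299 = 598 women and (20% + 10%) / 2 = 15% uptake. Contact numbers are assumed. Figure 1 lists possible contacts that sum to 12 + 4 + 4 + 1 + 2 + 3 = 26 (volunteer, health extension worker, antenatal, birth, postnatal, DPT), or 28 with six health extension worker visits. The background section reports that only 43% of women have any antenatal care, so means from 3 to 26 were used.

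**3. Slope when contacts have no effect.** Let Δ be the mean contacts of adopters minus non-adopters, and V the within-group variance of the count. Then approximately log(odds ratio per contact) = Δ / V.

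- Uptake adds no contact: Δ = 0, odds ratio 1.00.
- Half of adopters gain one, Δ = 0.5, Poisson: exp(0.5/3) = 1.18 and exp(0.5/26) = 1.02. Simulated: 1.17 and 1.02.
- The same with variance 3 × mean: exp(0.5/9) = 1.06 and exp(0.5/78) = 1.01. Simulated: 1.05 and 1.01.
- Half of adopters gain one and non-adopters gain one on average, Δ = −0.5, Poisson: about exp(−0.5/4) = 0.88 and exp(−0.5/27) = 0.98. Simulated: 0.87 and 0.98.

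These runs have no clustering and no covariates. With no true effect, bias arises only when uptake changes the contact count, and it can go either way.

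**4. Is pregnancy-only safe?** It restores the order of events, but an odds ratio of 1.00 under independent contacts holds by construction. Protocol objective 3a would use records to find women who need more prenatal counselling. Suppose half of women are targeted, each gains one pregnancy contact, and uptake is 10% against 20% in the rest, with no causal effect. The targeted share is 0.05/0.15 = 0.33 among adopters and 0.45/0.85 = 0.53 among non-adopters, so Δ = −0.20. With a base mean of 1, V is about 1.25 and the odds ratio about exp(−0.20/1.25) = 0.85. Over base means 1 to 12, and with a milder contrast (12% against 18%), simulation gave 0.85 to 0.99. Selection therefore remains.

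**5. Is cutting the count at uptake safe?** No. Take 6 pregnancy contacts, 0.75 per month after birth, and uptake spread evenly over 12 months. Non-adopters average 6 + 9 = 15 contacts; adopters, cut on average at month 6, have 6 + 4.5 = 10.5. With no effect at all, the simulated odds ratio was 0.72 to 0.74.

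**The case against.** The SAP describes the dose models as an association, and an association needs no time order. A contact at which counselling and supply happen together may be a real effect: Appendix 1 has health extension workers both counsel and provide methods. Restricting to pregnancy would drop the postpartum contacts that objective 1 covers. And if uptake leaves contact patterns unchanged, the no-effect slope is 1.00.

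Much of this stands. The association wording helps, but the stated objectives speak of effect, so the reading still needs guarding. Same-visit counselling and supply is not an error in itself; the problem is contacts after uptake and collection-only visits.

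A reader might infer more than the documents support:

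- *That the slope is certainly biased, or biased upward.* This depends on contact behaviour that the documents do not report. The highest simulated value, about 1.36 per contact, needs every adopter to gain a contact, Poisson spread and a mean of only 3.
- *That the count of contacts with family planning discussed is the worse of the two.* Not shown. The words on provision belong to the descriptive variable; a collection visit without discussion enters the total count, not this one.
- *That objective 3a shows extra postpartum follow-up of non-adopters.* It concerns prenatal counselling. Objective 3b, a monthly data review that includes uptake, is nearer, but does not state such follow-up either.

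**Conclusion.** The gap is real and should be fixed. The SAP applies temporal ordering to one outcome and omits it for the other in the same paragraph, so the primary-outcome dose counts contacts after uptake. The consequence is conditional: the slope is biased if uptake adds a visit or changes later contact frequency. Under the assumptions above, the odds ratio per contact with no true effect runs from 0.87 to 1.17, and is 1.00 if uptake changes nothing. The true size and sign are unknown. The adjusted arm comparison (SAP objective 1) and the 299 and 375 per arm do not use the contact count and are untouched.

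**What to change.** 1. State the contact window for the primary outcome. Add a dose model with pregnancy contacts only, adjusted for the planned confounders, and label the all-contacts model a descriptive association that includes contacts after uptake. This costs a short SAP statement, since the secondary outcome already requires the pregnancy/postpartum split. The model leaves out postpartum contacts and does not remove selection of who receives contacts, and the report should say so.
2. Where contacts are dated, enter cumulative prior contacts as a time-varying covariate in the planned hazards model, with and without the uptake visit. Including that visit admits collection-only visits; excluding it removes same-visit counselling effects. The two versions show the sensitivity but do not separate the explanations. Feasibility looks reasonable: the protocol plans chart review (section III.A), monthly follow-up and abstraction of health-worker data (Table 2) and a longitudinal register (Table 5), and Table 1 collects timing of adoption. Confirm that health extension worker and volunteer visits are dated.
3. Do not simply cut the count at uptake in the 12-month logistic model. Adopters then have less time to accumulate contacts, and the odds ratio is biased downward.

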Health providers (at Health Center)	Mixed methods questionnaire (going through each point of service – ANC, delivery, PNC and immunization)	
 • Integration of PFPF messages in ANC • Delivery of contraceptive methods at birth, including PPIUD, or in postnatal contacts • Experience with scheduling mobile services or referrals for permanent methods • Barriers to PFPF counseling and service delivery, including stock outs, organization of services, manpower, confidence to deliver, etc. • Experience with record keeping and analysis of PFPF data
District (woreda) health managers	Key Informant Interviews	
 • Attitudes towards PFPF integration; • Barriers/Facilitators • Experience with data reviews, analysis of data to address gaps • Experience addressing management or systems issues with FP service delivery
Pregnant and postpartum Women	Census of all pregnant women in the catchment area Questionnaire for all women 6-9 months pregnant F/U and re-interview all women 1 year later Review Integrated MCH/Family Health Card	
 • Attitudes and use of FP – past use, current use (once delivered) • Family support for FP, spouse, MIL, FIL (ask who are most influential) • Attitudes on immunization, facility delivery, plans for delivery, infant feeding, care seeking for self or sick baby • # of health contacts, # of ANC visits, place of delivery, PNC visits at facility or home, immunization visits, BF practices, return to fertility, timing of adoption of FP if adopted, rationale for not, what was most influential for those who did adopt (and didn't)

Study Population	Data Collection Method	Type of Information/Data Collected
		
 Perception of risk of pregnancy and motivation to avoid another pregnancy Experience with woman held card, if brought with them to all contacts with the system; was it helpful? Ability to communicate method choice without card
Registers, Referrals at Health Center, Health post level	(Revised longitudinal register)	Ability to track pregnant women's PFP counselling, decision making on method choice and uptake of PFP # of women in register, completeness of register Follow up mechanism

The Table 2 provides details on the general study timeline, program activities and study related activities.

Timeline	Program Activities	Research-related Tasks
Preparatory phase (1 st 4-6 months)	Woreda level engagement of stakeholders	

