We require a minimum of 299 women in postpartum observation period in each arm to detect an increase of at least 10% contraceptive prevalence rate (CPR) in the intervention arm, compared to the women in the control arm (20% vs 10% in the intervention and control arm, respectively) with $deff=1.5$ at 80% statistical power. Assuming about 20% lost-to-follow-up and non-response rate, we target to enroll 375 women in each arm. We consider that it will be sufficient to select 1 PHCU and its attached *kebeles* in each of the two *woredas* to ensure adequate sample size, with 2 PHCU randomly assigned to the intervention area (1 per *woreda*) and 2 to the control area (1 per *woreda*). The eligible women in 3rd trimester who consent to participate in the study voluntarily will be recruited and be interviewed at enrollment and at 12-month PP.

We used $p_1=0.2$ (20% PP contraceptive uptake by the final round of observation in the intervention arm) and $p_2=0.1$ (10% in the comparison arm). We considered $deff=(1+[m-1]\rho)= 1.5$. Because we are targeting 375 sample size of pregnant women in each arm consisting of 2 PHCUs, this implies $m=188$ AND $\rho=0.0027$.

Because the selected PHCUs are adjoining *woredas* of the same zone, it is expected that they will be quite similar, and in addition, the underlying population are all similar in terms of postpartum status; hence ρ very small (the larger the heterogeneity, the larger the ρ value). The Ethiopia DHS 2011 results suggest that the $deff$ of contraceptive use in all 11 regions are much smaller than the national level $deff$ of CPR (Appendix B – Estimates of Sampling Errors); *woreda* level $deff$ is expected to be much smaller due to less heterogeneity at *woreda* level, compared to the region/state level. In all regions, method specific $deff$ was <1.5 . So, we considered that of $deff=1.5$ is applied in this study is reasonable and practical. A study on postpartum use of contraceptive method at a *woreda* level in Ethiopia also had $deff=1.5$ (Abera Y, Mengesha ZB, Tessema GA. Postpartum contraceptive use in Gondar town, Northwest Ethiopia: a community based cross-sectional study. BMC Women's Health. 2015;15:19.)

Sample size requirements are included below based on the average number of providers and HDAs and managers in each *kebele*. See Table 4: Sample Size Summary

Table 4: Sample Size Summary

Study Participant	Intervention (2 PHCU)	Comparison (2 PHCU)	Total
Pregnant women	375	375	750

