Similarly, for focus group discussions with HDA, a waiver of signed informed consent allows for better protection of confidentiality as no identifiers will be collected, including signatures. Many of the HDAs have low or no literacy. The FGD will be recorded for ease in transcription and translation of the discussion, but any names or nicknames will be removed from the transcripts. FGDs will be audio recorded; recordings will be kept in a locked cabinet or room and will be destroyed after the study is complete and the file is closed.

2. Identify the countries where the research will take place, and the languages that will be used for the consent process.

Country	Consent Document(s) (adult consent, parental permission, youth assent, etc.)	Languages
Ethiopia	Consent	Amharic, Afan Oromo

C. Study Implementation:

See Table 5 for information on study implementation

Table 5: Study implementation procedures					
Study Population	Main Data Collection Method	Other Study Procedures	Number of contacts	Duration of Research Interview (Only)	Place of Interview
Health Extension Workers	Post intervention Questionnaire (covering each point of service – ANC, delivery, PNC & immunization)?	Orientation to study Training on PPFP counseling and promotion of PPFP to HDA Training on health records tools Monthly follow up	~19: Pre study training and start up (~3); monthly during study (15 months); Endline (1)	60 minutes	Health Post
Health providers (at Health Center)	Post intervention Questionnaire (covering each point of service – ANC, delivery, PNC & immunization)	Orientation to study Training on PPFP counseling Training on PPIUD and implants (subset of providers) Training on health records tools (and analysis?) Monthly follow up	~19: Pre study training and start up (~3); monthly during study (15 months); Endline (1)	60 minutes	Health Center
Health Development Army (HDA)/HDA team leaders	Post intervention Focus Group Discussions	Existing HEW/HDA contacts utilized for study activities.	1: FGDs	120 minutes	Health Post
District (woreda) health managers	Post intervention Key Informant Interviews	Orientation to study Ad hoc debrief on study monitoring	~6	45 minutes	Woreda Health Office
Pregnant and Postpartum Women	Pre-intervention questionnaire for all women 6-9 months pregnant Post intervention F/U questionnaire 6-9 months postpartum		2	Pre-Interview: 60 Post-Interview: 60	Household

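### The second dose-effect model uses FP discussions reported by the woman, mostly after she knows whether she adopted, so unequal recall could create or hide a dose-response; record-based and enrolment-report checks should be prespecified

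*SAP*

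**What the plan says.** SAP section A plans two dose-effect models, one on total contacts and one on "the number of contacts during which FP was discussed as reported by the woman". Both are run "on the primary and secondary outcomes, regardless of study arm". The primary outcome is "Proportion of interviewed postpartum women who used a modern family planning method within 12 months after giving birth". For the secondary outcome (a method chosen before delivery), only pregnancy contacts count.

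Protocol III.A states: "We will interview the women at study enrollment and at the end of the study". Section III.B places these interviews in the third trimester and a year after birth: "be interviewed at enrollment and at 12-month PP". Table 5 instead gives "Post intervention F/U questionnaire 6-9 months postpartum". The two follow-up times must be reconciled.

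On records, Protocol III.A says: "We will track women's contacts with the health system, particularly regarding PFP counseling, decision making and contraceptive adoption, through chart reviews". It adds that chart and record data from both arms will be analysed for differences in PPFP counselling. Table 5 lists review of the client-held card and twelve monthly abstractions at health posts and health centers. The SAP names none of these as a source for, or a check on, the FP-discussed dose. The service statistics in SAP section C concern uptake by method.

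**The concern.** Discussions at delivery, postnatal visits, immunization visits and postpartum home visits all fall after the enrolment interview. The woman can report them only at follow-up, in the interview that also serves the outcome. A woman who took a method may remember being told about it more readily than one who did not. The error in the dose then depends on the outcome, and adjustment for covariates or arm does not remove it. Because the model pools women across arms, the assigned contrast gives no protection either.

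Protocol Objective 1b and SAP objective 2 rest on the dose-effect models. A slope created by recall would be read as evidence that each additional FP discussion raises uptake.

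**Working it through.** **Planned sample size.** Protocol III.B inputs: 20% vs 10%, two-sided alpha 0.05, power 80%, deff 1.5. The protocol's formula without deff gives 198.96 per arm, rounded up to 199. Then 199 × 1.5 = 298.5, which rounds up to the stated 299. For enrolment, 299/0.80 = 373.75, so 374 against the stated 375. The plan's figure reproduces, and the analysable total is 2 × 299 = 598.

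**Analytic result.** Assumptions, none given in the documents:
- true FP discussions per woman are Poisson with mean μ and unrelated to adoption (no true effect);
- each discussion is recalled with probability q1 by adopters and q0 by non-adopters.

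Recalled counts are then Poisson with mean μq1 or μq0. The likelihood ratio for a recalled count x is (q1/q0)^x · exp(−μ(q1 − q0)), so

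logit P(adopted | x) = constant + x · ln(q1/q0).

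The false odds ratio per recalled contact is exactly q1/q0:
- 0.75/0.70 = 1.07
- 0.80/0.70 = 1.14
- 0.70/0.80 = 0.875

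**Simulation.** N = 598, 1000 runs per scenario, logistic regression of adoption on recalled count, no true effect. Ranges cover mean contacts of 2 or 4 and uptake of 15% or 40%. The 15% is the average of the protocol's 20% and 10%; the 40% and the mean contacts are assumptions.

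| Recall, adopters vs non-adopters | q1/q0 | Simulated OR per contact | p < 0.05 |
|---|---|---|---|
| 0.70 vs 0.70 | 1.00 | 1.00 | 4-6% |
| 0.80 vs 0.75 | 1.07 | 1.06-1.07 | 10-30% |
| 0.80 vs 0.70 | 1.14 | 1.14-1.15 | 29-80% |
| 0.80 vs 0.60 | 1.33 | 1.33-1.34 | 83-100% |
| 0.70 vs 0.80 | 0.875 | 0.87 | 26-79% |

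No design effect was applied. The simulated data have no clustering, so dividing z by √1.5 would lower the null rejection rate to 2 × (1 − Φ(1.96 × 1.2247)), about 1.6%. The other rates could then no longer be compared with 5%. Covariates are also left out. The table shows direction and order of size, not a forecast.

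**Limit of the illustration.** It treats the whole dose as recalled at follow-up. If part of the count comes from the enrolment interview, with recall unrelated to later adoption, the false odds ratio moves toward 1.

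**The case against.** The strongest reply is that nothing in the documents shows adopters recalling better. That stands: the direction is an assumption, and worse recall by adopters reverses the sign. A reader might infer that the bias must run upward; the documents do not support that.

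A reader might also infer that no restriction of contacts could help. The enrolment interview precedes birth, so discussions reported there cannot be coloured by postpartum adoption. Limiting the dose to them removes this mechanism for the primary outcome. It does not clearly do so for the secondary outcome, because a method may already have been chosen by enrolment.

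A third inference is that the SAP drops records from every dose model. The source of total contacts in the first model is not stated, and SAP section C brings stock-outs and counselling quality into the per-protocol analyses. Those are not counts of a woman's FP discussions, so they do not correct this dose, but the accurate statement is that records have no stated role in it. Nor does the register row of Table 1 commit registers as the dose source. Its entry, "Ability to track pregnant women's PFP counselling, decision making on method choice and uptake of PFP", sits beside register completeness and fits the feasibility objective. The commitment is in III.A.

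Finally, records are not a clean substitute. No passage shows FP discussions abstracted per woman and linked to study ID. Extra tracking tools go to intervention-site HEWs, and the SAP's supervision visits cover health posts only in the intervention arm. The visit at which a method is supplied may itself be logged as an FP contact, which would inflate a record-based slope. These points argue against replacing the recalled dose, but not against adding checks.

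**Conclusion.** The concern holds as a conditional one. Discussions after enrolment enter the second dose from the woman's report at a time when she knows her adoption status, and the SAP describes no check on recall. This is true at either stated follow-up time for a woman who has already adopted.

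If recall differs by adoption, the false odds ratio per contact is about the ratio of the recall rates. A ten-point gap (0.80 vs 0.70) gives 1.14 per contact, or (0.80/0.70)^3 = 0.512/0.343 = 1.49 across three contacts. False-positive rates are roughly 29-80% at a nominal 5%. These sizes rest on assumed recall rates, Poisson contacts, uptake of 15-40% and mean contacts of 2-4.

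A reader might extend this to the main result. That would be wrong: the arm comparison does not use this dose. What changes is how much SAP objective 2 and protocol Objective 1b can conclude from a slope in this model.

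**What to change.** In SAP section A, keep the recalled-dose model and prespecify these checks for the primary outcome:

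- **(a) Recorded dose.** Fit the same logistic model with the FP-contact count from registers and the client-held card, where records can be linked to study ID. Fit it within arm, because community recording differs by arm. Do not count the contact at which the method was supplied.
- **(b) Enrolment-reported dose.** Fit the model using only FP discussions reported at the enrolment interview.
- **(c) Agreement.** Tabulate recalled against recorded FP contacts by adoption status.

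State in advance that a slope seen only with contacts recalled at follow-up will be reported as possibly due to recall bias. Also state which interview supplies each part of the recalled dose, and the source of total contacts in the first model.

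The cost is SAP wording, two further models and a table, on data the protocol already plans to collect. Woman-level linkage must be confirmed first. Incomplete records will flatten the slope in (a), each within-arm model has about half the sample (299 of 598), and (b) omits later contacts. A flat slope in (a) or (b) alone would therefore not show that there is no dose-response.
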